5.0 Subject Disposition

The number of subjects for each of the following categories will be summarized in Period 1, for overall and for each treatment group in ITT_1 Population:

- Subjects randomized;
- Subjects who took at least one dose of study drug in Period 1;
- Subjects who completed Period 1;
- Subjects who completed study drug in Period 1;
- Subjects who prematurely discontinued from study in Period 1;
- Subjects who prematurely discontinued study drug in Period 1;

The summary will also be provided for Period 2 for each of the following categories and by treatment groups in the ITT_2 Population:

- Subjects who entered Period 2;
- Subjects who took at least one dose of study drug in Period 2;
- Subjects who completed study;
- Subjects who completed study drug in Period 2;
- Subjects who prematurely discontinued from study in Period 2;
- Subjects who prematurely discontinued study drug in Period 2.

Number and percentage of subjects who discontinue study drug or who discontinue from study will be summarized by primary reason for each treatment group and overall.

In addition, the above summaries (except for the reason for premature discontinuation) will also be summarized by center in the accountability table.

6.0 Study Drug Duration and Compliance

For Safety_1/Safety_2 Population, duration of treatment will be summarized for each treatment group in Period 1 and Period 2. For ALL_UPA Population, duration of treatment will be summarized overall and for each upadacitinib dose group. Duration of treatment is defined as follows:

Period 1:

For subjects who did not continue into Period 2:

- Date of last dose of study drug in Period 1 – Date of first dose of study drug in Period 1 + 1.

For subjects who continued into Period 2:

- Minimum of (Date of first dose of study drug in Period 2 – Date of first dose of study drug in Period 1, Date of last dose of study drug in Period 1 – Date of first dose of study drug in Period 1 + 1.)

Period 2:

For subjects who continued into Period 2:

- Date of last dose of study drug in Period 2 – Date of first dose of study drug in Period 2 + 1.

ALL_UPA:

Study drug duration during the administration of study drug in ALL_UPA Population is defined as:

- Date of last dose of upadacitinib – Date of first dose of upadacitinib + 1.

Duration of treatment will be summarized using the number of subjects treated, mean, standard deviation, median, minimum and maximum. In addition, the number and percentage of subjects in each treatment duration interval (≥ 4 weeks, ≥ 12 weeks, ≥ 24 weeks, ≥ 36 weeks, ≥ 48 weeks) will be summarized for ALL_UPA Population.

Treatment compliance for Period 1 and 2 will be summarized by treatment groups for Safety Populations (Safety_1 and Safety_2). For ALL_UPA Population, treatment compliance will be summarized overall and for each upadacitinib dose group. Treatment compliance is defined as the number of tablets actually taken divided by the number of tablets that should have been taken. For subjects who prematurely discontinued the study drug, the planned tablets will only be counted prior to that scheduled visit of discontinuation. Percent compliance will be summarized.

7.0 Demographics, Baseline Characteristics, Medical History, and Prior/Concomitant Medications

Demographics, baseline or disease characteristics, and medical history will be summarized for the ITT_1 Population overall and by treatment groups. Prior medications will be summarized for the Safety_1 Population overall and by treatment groups. Concomitant medications will be summarized for the Safety_1 and Safety_2 Populations overall and by treatment groups. Categorical variables will be summarized with the number and percentage of subjects; percentages will be calculated based on the number of non-missing observations. Continuous variables will be summarized with descriptive statistics (number of non-missing observations, mean and standard deviation, median, minimum and maximum).

7.1 Demographics and Baseline Characteristics

Continuous demographic variables include age, weight, height, and body mass index (BMI). Categorical demographic variables include sex, ethnicity, race, country, age (≤ 50 and > 50), weight (< 60 or ≥ 60 kg), BMI (< 25 , ≥ 25 - < 30 or ≥ 30 kg/m²), tobacco user (current, former, never, unknown), and alcohol user (current, former, never, unknown).

Disease characteristics include the following Baseline F-VASI, Baseline T-VASI, Baseline VitiQoL total score and each domain score, Baseline VES, Baseline HADS, vitiligo disease diagnosis duration in years as continuous variables and Baseline VNS, Baseline DLQI, Baseline F-PhGVA, Baseline T-PhGVA, Baseline F-PaGVA, Baseline T-PaGVA, subject Fitzpatrick skin type, history of vitiligo-related symptoms (increased sensitivity, itch, and pain), status of active vitiligo, Baseline T-VASI (≤ 10 and > 10) as categorical variables.

7.2 Medical History

Medical history data will be coded using the Medical Dictionary for Regulatory Activities (MedDRA). The actual version of the MedDRA coding dictionary will be noted in the

statistical tables and clinical study report. The number and percentage of subjects in each medical history category (by MedDRA system organ class and preferred term) will be summarized overall and by treatment groups in the Intent-to-Treat Population in Period 1 (ITT_1). The system organ class (SOC) will be presented in alphabetical order, and the preferred terms will be presented in alphabetical order within each SOC. Subjects reporting more than one condition/diagnosis will be counted only once in each row (SOC or preferred term).

7.3 Prior and Concomitant Medications

Prior and concomitant medications will be summarized by generic name in the Safety population. A prior medication is defined as any medication taken prior to the date of the first dose of study drug and will be summarized in Period 1. For Period 1 and 2, a concomitant medication in each period is defined as any medication that started prior to the date of the first dose of study drug in each period and continued to be taken after the first dose of study drug in each period or any medication that started on or after the date of the first dose of study drug in each period, but not after the date of the last dose +1 of study drug in each period. The number and percentage of subjects taking medications will be summarized by generic drug name based on the World Health Organization (WHO) Drug Dictionary for both prior and concomitant medications.

In addition, subjects' prior exposure to topical treatment (topical corticosteroid [TCS], topical calcineurin inhibitor [TCI]), systemic corticosteroids, phototherapy, procedure, and other will be summarized for each treatment group.

8.0 Handling of Potential Intercurrent Events for the Primary Endpoint

The primary efficacy endpoint of percent change in F-VASI at Week 24 (defined in Section 3.1) will be analyzed based on the ITT_1 Populations. For treatment policy strategy, the occurrence of the intercurrent event (treatment discontinuation) is considered as irrelevant in defining the treatment effect of interest. Under this strategy, the value for the variable of interest is used regardless of whether or not the intercurrent event occurs.

9.0 Efficacy Analyses

9.1 General Considerations

All efficacy analyses will be conducted in the ITT Population in each period (ITT_1 and ITT_2). All tests will be 2-sided at an alpha level of 0.1.

The Primary Analysis will be performed after all ongoing subjects have completed Week 24 or have prematurely discontinued prior to Week 24, data pertaining to Period 1 has been cleaned, and the database has been locked. This will be the only and final analysis for the efficacy endpoints in Period 1.

For analysis in Period 1, continuous endpoints and categorical endpoints will be analyzed using Mixed-Effect Model Repeat Measurement (MMRM) and Cochran-Mantel-Haenszel (CMH), respectively.

The analysis models and imputation methods for categorical and continuous endpoints in Period 1 and Period 2 are summarized in the following table:

Table 1. Analysis Models and Imputation Methods

Period	Type of Variables	Imputation Method	Intercurrent Events Handling	Analysis Model
Period 1	Continuous	MMRM ^a	The treatment policy strategy is used in this study. Under this strategy, all values for the variable of interest are used regardless of the intercurrent event.	MMRM model includes treatment, visit and treatment by visit interaction, stratification factors (age group [≤ 50 and > 50] ^e , baseline disease severity [T-VASI < 15 and ≥ 15] ^d , and status of active vitiligo [Yes/No]), and baseline measurement
	Categorical	NRI-MI ^b	The treatment policy strategy is used in this study. Under this strategy, all values for the variable of interest are used regardless of the intercurrent event.	CMH test adjusting for stratification factors (age group [≤ 50 and > 50], baseline disease severity [T-VASI < 15 and ≥ 15], and status of active vitiligo [Yes/No])
Period 2	Continuous	AO ^c	The treatment policy strategy is used in this study. Under this strategy, all values for the variable of interest are used regardless of the intercurrent event.	ANCOVA includes treatment, stratification factors (age group [≤ 50 and > 50], baseline disease severity [T-VASI < 15 and ≥ 15] ^d , and status of active vitiligo [Yes/No]), and baseline measurement
	Categorical	AO ^c	The treatment policy strategy is used in this study. Under this strategy, all values for the variable of interest are used regardless of the intercurrent event.	Descriptive summary

CMH = Cochran-Mantel-Haenszel; ANCOVA = Analysis of Covariance

- Mixed-Effect Model Repeat Measurement.
- Non-Responder Imputation while incorporating Multiple Imputation (MI) to handle missing data due to COVID-19 or any other missing data that can be reasonably assumed to be Missing at Random.
- As observed (AO): The AO analysis will not impute values for missing evaluations, and thus a subject who does not have an evaluation at a scheduled visit will not be included in the AO analysis for that visit.
- The stratification factor of baseline disease severity (T-VASI < 15 and ≥ 15) will not be included in model for percent change from Baseline in T-VASI.
- If the MMRM model cannot converge, the stratification factor of age will not be included in the model.

To evaluate long-term efficacy, all endpoints (categorical and continuous) will be summarized descriptively at each visit by treatment groups overall and by stratification factors.

Analysis of Continuous Variables

In Period 1, the Baseline means and visit means will be presented for each treatment group who have both Baseline and post-baseline visit values. Change (and/or percent change) from Baseline in the treatment groups will be compared using MMRM as described in [Table 1](#). Point estimates, SE, and 95% confidence interval (CI) of LS mean change (and/or percent change) from Baseline within treatment groups, along with p-values between each upadacitinib treatment group and placebo will be provided. MMRM will be the primary approach to handle missing data for continuous endpoints (Section [9.2](#)) in Period 1. In addition, the primary efficacy endpoint will be analyzed using MI defined in Section [9.2](#) as the sensitivity analysis.

For long-term efficacy, the raw value at Baseline and each visit will be summarized using mean for each of the 5 treatment groups as observed. For change (and/or percent change) from Baseline, LS mean, SE, and 95% CIs generated by ANCOVA by visit as described in [Table 1](#). Descriptive summary statistics including median, Q1, Q3, minimum and maximum of change (and/or percent change) from Baseline will also be provided.

Analysis of Categorical Variables

In Period 1, frequencies and percentages will be provided along with 95% CIs. Point estimates, 95% CIs and p-values from the CMH test for the difference in proportions between each upadacitinib group and placebo will be provided. Breslow-Day test will be performed to test the homogeneity between strata.

Non-Responder Imputation while incorporating Multiple Imputation (MI), NRI-MI, will be the primary approach to handle missing data for categorical endpoints in Period 1 (Section [9.2](#) and [Appendix E](#)).

- If there are missing data due to COVID-19 or any other missing data that can be reasonably assumed to be Missing at Random, a total of 30 datasets will be generated by PROC MI, and subjects will be characterized as responders or non-responders based on MI imputed values.
 - If not all the imputed datasets are identical, analysis will be performed as described in [Appendix E](#).
 - If all the 30 imputed datasets are identical, all statistical inferences will be calculated using the first imputed dataset: 1) The corresponding 95% CIs will be constructed based on normal approximation to the binomial distribution. 2) Adjusted differences, 95% CIs and p-values for the comparisons between each upadacitinib group and placebo will be calculated based on CMH test adjusting for stratification factors.
- If there are no missing data due to COVID-19 or any other missing data that can be reasonably assumed to be Missing at Random, the NRI-MI method will be the same as traditional NRI method. All statistical inferences will be calculated using the NRI imputed datasets.

For long-term efficacy, descriptive summary statistics including frequencies and percentages for categorical endpoints, along with 95% CIs based on normal approximation, will be provided based on as observed data.

Unless otherwise specified, any subject who is randomized based on a wrong stratum will be analyzed according to the actual stratum the subject belongs to.

"Baseline" refers to the last non-missing observation before the first administration of study drug or randomization if no study drug is given.

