2.2 Study Design Overview

This is a Phase 2, multicenter, randomized, double-blinded, parallel-group, placebo-controlled dose-ranging study that will evaluate the safety and efficacy of upadacitinib in adult subjects \geq 18 to 65 years of age with NSV. The study is comprised of a 35-day Screening Period, a 24-week double-blind treatment period (Period 1), a 28-week blinded long-term extension (Period 2), and a 30-day Follow-up Period.

Subjects who meet eligibility criteria at Baseline will be randomized in a 2:2:2:1:1 ratio to one of five treatment groups:

[figure not shown]
- Group 1: upadacitinib 22 mg once daily (QD) (N = 40) (Period 1) → upadacitinib 22 mg QD (Period 2)
- Group 2: upadacitinib 11 mg QD (N = 40) (Period 1) → upadacitinib 11mg QD (Period 2)
- Group 3: upadacitinib 6 mg QD (N = 40) (Period 1) → upadacitinib 6 mg QD (Period 2)
- Group 4: placebo (N = 20) (Period 1) → upadacitinib 22 mg QD (Period 2)
- Group 5: placebo (N = 20) (Period 1) → upadacitinib 11 mg QD (Period 2)

At Week 24, subjects who were randomized to placebo at Baseline will be switched to either upadacitinib 22 mg (Group 4) or upadacitinib 11 mg (Group 5) in a blinded fashion per pre-specified randomization assignments.

The AbbVie study team will be unblinded to perform the Week 24 primary analysis. The unblinding will take place after all subjects have completed the Week 24 visit or have prematurely discontinued prior to Week 24. Sites and subjects will remain blinded throughout the study.

The schematic of the study is shown in [Figure 1](#).

Figure 1. Study Schematic

BL = Baseline; F-VASI = Facial Vitiligo Area Scoring Index; PBO = placebo; QD = once daily; UPA = upadacitinib

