2.4 Sample Size Determination

Assuming a Week 24 percent change from Baseline in F-VASI of 0% in the placebo arm, a conservative estimate based on a prior study in vitiligo,¹ the planned total sample size of 160 subjects (40 subjects in each upadacitinib group, 40 subjects in total in the placebo groups) will provide more than 90% power to detect the treatment difference of 40% reduction (assuming a standard deviation of 54.8%) in at least 1 upadacitinib group versus placebo using a 2-sided significance level of 0.1 based on the two-sample t-test.

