4.0 Analysis Populations

The following Intent-to-Treat (ITT) populations will be used for the analyses.

- The ITT Population in Period 1 (ITT_1) includes all randomized subjects in Period 1. Subjects will be included in the analysis according to the treatment groups that they are randomized to. Analyses will include the following 4 groups: upadacitinib (UPA) 22 mg QD, UPA 11 mg QD, UPA 6 mg QD and placebo.
- The ITT Population in Period 2 (ITT_2) includes all subjects entered Period 2. Subjects will be included in the analysis according to the 5 treatment groups that they are randomized to at baseline: UPA 22 mg QD-> UPA 22 mg QD, UPA 11 mg QD-> UPA 11 mg QD, UPA 6 mg QD-> UPA 6 mg QD, Placebo-> UPA 22 mg QD and Placebo-> UPA 11 mg QD.

- The ITT_1/ITT_2 Populations will be used for all efficacy analyses across Period 1/Period 2.

The following three Safety Populations will be used for the safety analysis:

- The Safety Population in Period 1 (Safety_1) is defined as all subjects who are randomized and received at least one dose of study drug in Period 1. Subjects will be summarized in the following 4 groups: UPA 22 mg QD, UPA 11 mg QD, UPA 6 mg QD and placebo, based on the treatment actually received (defined as the most frequent dose regimen received in Period 1).
- The Safety Population in Period 2 (Safety_2) is defined as all subjects received at least one dose of study drug in Period 2. Subjects will be included in the 5 groups same as which they were randomized to at baseline: UPA 22 mg QD-> UPA 22 mg QD, UPA 11 mg QD-> UPA 11 mg QD, UPA 6 mg QD-> UPA 6 mg QD, Placebo-> UPA 22 mg QD and Placebo-> UPA 11 mg QD.
- The all upadacitinib treated (ALL_UPA) Population is defined as subjects who received at least one dose of upadacitinib in the study. Subjects will be analyzed based on the treatment actually received: UPA 22 mg QD, UPA 11 mg QD and UPA 6 mg QD.

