9.5 Additional Efficacy Analyses

In Period 1, unless otherwise specified, additional efficacy endpoints will be compared between the each upadacitinib treatment group and placebo. The categorical endpoints and continuous endpoints will be analyzed by CMH and MMRM, respectively, and the analyses are specified in Section 9.1 and Section 9.2. Proportion of subjects selecting each of the 16 VitiQoL questions will be summarized for each of the 16 questions by response categories at each visit as observed.

In Period 2, the categorical endpoints will be summarized by treatment groups as observed, and the continuous endpoints will be analyzed as observed using ANCOVA as described in Table 1. The analyses are specified in Section 9.1 and Section 9.2.

In Addition, at the time of the Primary Analysis, additional long-term analysis up to Week 52 will be provided for the below variables among all subjects who may potentially reach to Week 52 by the data cutoff using NRI-MI (categorical variables) or MMRM (continuous variables):

- F-VASI 50, F-VASI 75,
- T-VASI 50,
- Percent change from Baseline in F-VASI,
- Percent change from Baseline in T-VASI

At the time of the final analysis, the above variables will be evaluated up to Week 52 using NRI-MI (categorical variables) or MMRM for the continuous variables.

In addition, for VitiQoL, VNS, DLQI and HADS, analyses will be performed, for up to Week 52, for the following:

- Change from Baseline in VitiQoL question 16 regarding the severity of skin condition.
- Proportion of subjects selecting each of the response categories of VNS
- Change from Baseline in Dermatology Life Quality Index (DLQI) total score
- Achievement of a clinically meaningful improvement in DLQI total score defined as $\Delta \text{DLQI} \geq 4$ (for subjects with $\text{DLQI} \geq 4$ at baseline)
- Achievement of a clinically meaningful improvement in HADS anxiety and depression scores defined as $\Delta \text{HADS} \geq 1.5$ (for subjects with $\text{HADS} \geq 1.5$ at baseline)

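### Single-group response-rate intervals use the normal approximation with no low-count rule: always in the long-term output, and in one branch of Period 1 (minor, descriptive output only)

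*SAP*

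**What the plan says.** SAP 9.1, under the analysis of categorical variables, makes single-group intervals planned output: "In Period 1, frequencies and percentages will be provided along with 95% CIs". The method then depends on the missing data.

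- **Data treated as missing at random exist, and all 30 imputed datasets are identical:** "The corresponding 95% CIs will be constructed based on normal approximation to the binomial distribution".
- **Such data exist, but the imputed datasets differ:** the SAP refers to Appendix E. That appendix covers the CMH treatment difference and its pooling by Rubin's formula. It gives no single-group interval.
- **No such data:** inference uses the non-responder-imputed dataset. No single-group interval method is named.

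For long-term efficacy there is no branching. Frequencies and percentages are given "along with 95% CIs based on normal approximation, will be provided based on as observed data". SAP 9.5 agrees on the scope: "In Period 2, the categorical endpoints will be summarized by treatment groups as observed".

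Planned sizes are "40 subjects in each upadacitinib group, 40 subjects in total in the placebo groups" (SAP 2.4), and SAP 4.0 pools placebo in Period 1. In Period 2 the placebo subjects split into two switch groups of 20 (SAP 2.2).

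Neither document gives an exact or score interval, a truncation rule or a minimum responder count. Protocol 7.4 asks only for a 95% interval of the treatment effect.

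**The concern.** The normal-approximation interval takes its width from the observed proportion. With no responders the estimated standard error is zero, so the interval has no width. With a few responders it is symmetric about a value close to zero and runs below zero.

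Groups of 40 and 20 are small enough for this to appear in printed tables. The SAP summarizes strict responder definitions by visit (F-VASI 90, T-VASI 75, T-VASI 90), and VASI is assessed from Week 2, so cells with 0 to 3 responders are plausible. In such a cell the table would claim no uncertainty or show an impossible value.

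In Period 2, SAP Table 1 plans only a descriptive summary for categorical endpoints. There this interval is the planned statement of precision, except for the three endpoints that SAP 9.5 also evaluates to Week 52 by NRI-MI (F-VASI 50, F-VASI 75 and T-VASI 50).

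**Working it through.** **Inputs.** n = 40 per Period 1 group (SAP 2.4, 4.0). In Period 2, n is at most 40 in each continuing dose group and at most 20 in each placebo-switch group (SAP 2.2); as-observed analysis can only lower these. 95% level, z = 1.96 (z² = 3.8415). Assumption: normal approximation means the Wald interval without continuity correction.

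**The plan's own figures.** The plan prints no interval, so there is none to reproduce. Its power statement does reproduce: difference 40, SD 54.8, 40 v 40, two-sided 0.1 gives 94.4% (noncentral t, 78 df), in line with more than 90%. This point does not depend on it.

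**Step 1: no responders.** The interval is p ± z·√(p(1−p)/n). At p = 0 the half-width is 0, so it is 0% to 0%. The Clopper-Pearson upper limit is 1 − 0.025^(1/n): 8.8% at n = 40 and 16.8% at n = 20.

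**Step 2: negative lower limits.** For x responders the lower limit is below zero when 0 < x < n·z²/(n + z²).

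- n = 40: 40 × 3.8415 / 43.8415 = 3.50
- n = 20: 20 × 3.8415 / 23.8415 = 3.22

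So x = 1, 2 and 3 fail at both sizes. Example, 3/40: √(0.075 × 0.925 / 40) = 0.0416; 1.96 × 0.0416 = 0.0816; 7.5% − 8.16% = −0.66%.

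| Responders | Wald, n=40 (%) | Clopper-Pearson, n=40 (%) | Wald, n=20 (%) | Clopper-Pearson, n=20 (%) |
|---|---|---|---|---|
| 0 | 0 to 0 | 0 to 8.81 | 0 to 0 | 0 to 16.84 |
| 1 | −2.34 to 7.34 | 0.06 to 13.16 | −4.55 to 14.55 | 0.13 to 24.87 |
| 2 | −1.75 to 11.75 | 0.61 to 16.92 | −3.15 to 23.15 | 1.23 to 31.70 |
| 3 | −0.66 to 15.66 | 1.57 to 20.39 | −0.65 to 30.65 | 3.21 to 37.89 |
| 4 | 0.70 to 19.30 | 2.79 to 23.66 | 2.47 to 37.53 | 5.73 to 43.66 |

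High counts mirror this. The upper limit passes 100% at 37 to 39 of 40 (100.66%, 101.75%, 102.34%) and at 17 to 19 of 20 (100.65%, 103.15%, 104.55%). The width is zero at 40/40 and 20/20.

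**Step 3: coverage.** The documents state no responder rates, so the true rate is an assumed range. Coverage at a given rate is the sum of the binomial probabilities of all counts whose interval contains that rate. The means below average this over a fine grid of rates from 1% to 10%.

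| Method | Mean, n=40 | Mean, n=20 | Minimum, n=40 | Minimum, n=20 |
|---|---|---|---|---|
| Wald | 79.0% | 62.7% | 33.1% | 18.2% |
| Wilson | 95.6% | 95.7% | 89.5% | 89.4% |
| Clopper-Pearson | 98.4% | 98.8% | 95.3% | 97.5% |

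Over rates of 10% to 20%, mean Wald coverage is 91.8% (n = 40) and 89.1% (n = 20). At a rate of 18% it is 94% and 88%. Over 18% to 50% at n = 40 the mean is 93.5%, with a minimum of about 89% near 19.3%.

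**The case against.** **Period 1 reach.** A reader might infer that every Period 1 single-group interval is a Wald interval. The SAP does not say so. It names the method for one branch only and names none for the other two. Only the long-term sentence is unconditional. This objection stands and sets the scope of the point.

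**Strata.** SAP 9.1 also says that long-term "all endpoints (categorical and continuous) will be summarized descriptively at each visit by treatment groups overall and by stratification factors". One might infer still worse intervals in stratum cells; in an assumed cell of 10, for example, 0 responders would print 0% to 0% against an exact upper limit of 30.8%. But that sentence does not mention intervals, the interval sentence does not mention strata, and no cell sizes are given. The figure is illustrative and carries no weight here.

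**Frequency.** How often low counts occur cannot be shown from the documents. If percent change were normal with the planning values (40-point reduction, SD 54.8), active-arm rates would be about 43% for F-VASI 50 and 26% for F-VASI 75. Wald coverage would then be 94.5% and 95.1% at n = 40, and 93.2% and 90.5% at n = 20. Period 2 has no placebo arm. The same crude assumption with 0% mean change gives placebo about 8.6% for F-VASI 75 and 5.0% for F-VASI 90. The chance of 3 or fewer responders among 40 is then about 55% and 86%. Low counts are therefore plausible in some cells and unlikely in others.

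**Reading of the method.** The SAP does not say whether a continuity correction or truncation applies, so Wald is an interpretation. Truncating at 0% would hide the negative limits but would not cure the zero width or the under-coverage.

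**Materiality.** Counts are printed beside the intervals, and no test uses them. This also stands, and it is why the point is minor.

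**Conclusion.** The point holds as a minor one. The plan specifies an interval that fails in low-count cells and provides no alternative. This is unconditional for the long-term as-observed summaries and conditional for Period 1. The zero width at 0 responders and the negative limits at 1 to 3 responders need no assumed rate, only the Wald reading and the planned sizes. With attrition, the negative limit at 3 responders persists down to n = 14. The coverage figures do rest on assumed rates: severe under-coverage is confined to low rates (or, by symmetry, very high ones), and is worse at n = 20 than at n = 40.

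A reader might go further and infer that the responder comparisons with placebo are compromised. The documents do not support that. Those comparisons use the CMH adjusted difference with its own interval and p-value, and the primary endpoint is continuous and analysed by MMRM. MCP-Mod and the sample size do not use these intervals either.

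**What to change.** In SAP 9.1, replace the normal approximation with Clopper-Pearson for single-group response-rate intervals in two places: the long-term sentence and the Period 1 branch with identical imputed datasets. Add the same method for Period 1 when no data are treated as missing at random and the non-responder-imputed dataset is used.

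Leave the pooled Appendix E analysis of the treatment difference as it is. The branch with differing imputed datasets will still have no named single-group interval, and this change does not supply one.

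The cost is two wording replacements and one added sentence. Clopper-Pearson is conservative and somewhat wider: 20.9 against 18.6 points at 4/40. Wilson is an acceptable alternative. It is not always wider than Wald (30.8 against 31.3 points at 3/20; 33.5 against 35.1 at 4/20), but its coverage dips to about 89% at low rates at both sizes. Whichever is used, the SAP should name one method.
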